The reimbursement amounts were suggested by the clinical lead and his team and are based on clinical trials conducted at ACSA with the same target patient population over the last 5 years. These amounts have also been reviewed by the local Peruvian ethics committee (latest communication included as an attachment in the Additional Information Section). Patients will be recruited from 14 villages that have health posts in the districts of Iquitos, San Juan Bautista, and Punchana. Some are located along the road and others at the edges of the rivers. The distance by land or river to the city of Iquitos is less than 1.5 hours, most less than 1 hour. In general, the people who live in these recruitment areas are representative of the general population that suffers malaria in the Amazon region. They are generally mestizo and do not live in extreme poverty. However, they do depend on daily wages to support their family and most do not have personal vehicles and therefore must hire a combination of water taxi and rickshaw drivers to travel to the clinical site.

Costs to Subjects: Describe any costs for care associated with research (including a breakdown of standard of care procedures versus research procedures), costs of test drugs or devices, and research procedure costs that are the subject's responsibility as a consequence of participating in the research. Describe any offer for reimbursement of costs by the sponsor for research related injury care.

There will be no cost to subjects for participating in the trial. They may incur lost wages and travel costs when staying at the clinic or visiting test site for follow-up visits and they will be reimbursed as outlined above.

Data and Safety Monitoring: The IRB requires review and approval of data and safety monitoring plans for greater than minimal risk research, clinical research, or NIH-funded/FDA-regulated clinical investigations.

If you are conducting greater than minimal risk research, clinical research, or your clinical investigation is NIH-funded/FDA-regulated, describe your Data and Safety Monitoring Plan (DSMP). Click here for additional guidance on developing a Data and Safety Monitoring Plan.

If this is a *non-sponsored investigator-initiated* protocol considered greater than minimal risk research, clinical research, or your clinical investigation is FDA-regulated, *and* if you are planning on using a Data and Safety Monitoring Board (DSMB) as part of your DSMP, click here for additional guidance for information to include with your IRB application.

If relying on an independent agent or committee for DSMB services, it is the PI's responsibility to establish the services with the agent or committee. Please be reminded that the PI must submit DSMB reports to the IRB via modification or continuing review.

We have contracted Covance to oversee Peruvian work, including regulatory submissions, medical and safety monitoring, pharmacovigilance, and site monitoring.

The occurrence of an AE or SAE may come to the attention of study personnel during study visits and interviews of a study participant presenting for medical care, or upon review by a study monitor. All AEs including local and systemic reactions not meeting the criteria for SAEs will be captured on the appropriate CRF. Information to be collected includes event description, time of onset, clinician's assessment of severity, relationship to study product (assessed only by those with the training and authority to make a diagnosis), and time of resolution/stabilization of the event. All AEs occurring while on study must be documented appropriately regardless of relationship. All AEs will be followed to adequate resolution.

All SAEs, occurring after the signing of the ICF until the End of Study visit or up to 42 days after last dose of study drug, and regardless of study drug relationship, must be reported, within 24 hours of obtaining knowledge of the event, to the Contract Research Organization (CRO). The CRO will inform the Sponsor on the same day.

The SAE form will collect data surrounding the event (e.g. the nature of the symptom[s], time of onset in relation to initiation of therapy, duration, intensity, and whether or not therapy was interrupted or discontinued). The Investigator's assessment of the probable cause of the event will also be included. In addition, relevant medical history, concomitant medications, laboratory and diagnostic tests reports, and procedures as well as all pertinent medical information related to the event will also be collected.

The investigator or study site personnel will provide the initial notification by completing the SAE page in the eCRF. The SAE form must include the investigator's assessment of the relationship of the event to the study drug and must include the investigator's signature. Even if minimal information is available, it is imperative that the investigator always makes an assessment of causality, as causality assessment is one of the requirements for regulatory reporting. Based on the follow up information received the investigator can change his/her causality assessment and amend the SAE form accordingly.

Covance Pharmacovigilance will forward SAE queries directly to the investigator requesting additional information. It is the investigator's responsibility to be diligent in providing this information as soon as it is available.

If an event meets serious criteria and it is not possible to access the EDC, the SAE will be submitted electronically using this email address: [contact] or [contact]. If email access is not available, the SAE will be reported telephonically using a toll free number corresponding to the country (see Safety Management Plan)

If Covance Pharmacovigilance becomes aware of the case via a telephone call, the pharmacovigilance representative will document the event details on a telephone contact log which will be filed with the case. A request for a completed SAE form will be emailed to the Investigator site and the Covance Project Manager and Site Monitor will be notified.

Dates should be recorded in the DD/MMM/YYYY format, e.g. 01/JAN/2012. All personal health identifying information (PHI) must be deleted, which may identify the patient from supporting documents. (e.g. patient name, address). The investigator or study site personnel to call the site monitor with any questions regarding the completion of the SAE form.

All SAEs will be followed until satisfactory resolution or until the site investigator deems the event to be chronic or the adherence to be stable.

It is the responsibility of the Sponsor to determine whether a reported SAE fits the classification of a SUSAR and to notify the investigator of their decision as soon as possible. It is the responsibility of the Sponsor to determine whether an event requires expedited reporting and to notify the investigator of their decision as soon as possible.

Any SAE/SAR/SUSAR, irrespective of causality assessment to study drug and expectedness per IB, must be reported to the Regulatory Authority by University of Kentucky or delegate and to the relevant EC by the PI or delegate within 7 calendar days after the Sponsor becomes aware of the event. If the initial report is incomplete, a complete report must be submitted within 8 days of sending the first response. If significant new information is received by University of Kentucky on a case already reported, the clock starts again, and this should be provided as a follow-up report within 15 calendar days of receipt of the information.

A SUSAR that is not fatal or life-threatening must be reported to the Regulatory Authority by University of Kentucky or delegate and to the EC by the PI or delegate and in any event within 15 calendar days after University of Kentucky first becomes aware of the event.

SAEs/SARs/SUSARs must be recorded and reported whether or not the investigator considers the SAE/SARs/SUSAR to be related to SJ733.

Photocopies of results, consultant report(s), a summary of the outcome of the reaction and the investigator's opinion of SJ733 relationship to the SAE/SUSAR will accompany the SAE form if and when available.

If any information relating to the study drug in a study becomes available after the submission of a final protocol to the competent authority, which may impact on the conduct of the study, including but not limited to the risk and benefit evaluations underpinning approvals and volunteers consent, University of Kentucky will notify the Investigator in writing as soon as practically possible and the parties will agree, in writing, what steps need to be taken, if any.

The Investigator will be required to provide the following information:

Patient's ID number, date of birth and gender

Description of the event

53333

o Date, time of onset

- o Clinical history
- o Associated signs and symptoms
- o Temporal association with the study drug
- o Medical management, including rationale
- o Pertinent laboratory tests
- o Severity (see definition or toxicity score)
- o Causal relationship to the study drug with investigator's rationale for causality assessment
- Other information
- o Relevant past medical history
- o Concomitant medications
- o Autopsy report or expectation of an autopsy in the case of death
- Outcome of the event
- o Date, time of resolution, if resolved
- Documentation of notification to the EC by the Investigator

Any medical condition that is present at the time that the participant is screened will be considered as baseline and not reported as an AE. However, if the study participant's condition deteriorates at any time during the study, it will be recorded as an AE. UPs will be recorded in the data collection system throughout the study.

Changes in the severity of an AE will be documented to allow an assessment of the duration of the event at each level of severity to be performed. AEs characterized as intermittent require documentation of onset and duration of each episode.

The PI will record all reportable events with start dates occurring any time after informed consent is obtained until 7 (for non-serious AEs) or 30 days (for SAEs) after the last day of study participation. At each study visit, the investigator will inquire about the occurrence of AE/SAEs since the last visit. Events will be followed for outcome information until resolution or stabilization.

Additionally the Study will have an SRT and DSMB. The members of the Safety Review Team (SRT) are responsible for decisions related to the safety of patients and the continuation of the study. The SRT will assess preliminary safety, efficacy and pharmacokinetic data (if available) up to Day 14 of the first four patients enrolled, and thereafter upon completion of Day 14 assessments of each cohort and whenever else indicated as a result of safety concerns. The SRT will decide on the appropriateness of subsequent doses to be administered and continuation of the study.

The SRT will consist of the following people:

- the Principal Investigator (clinical lead [name])
- the Sponsor ([name])
- the Medical Monitor
- the Project Director

The SRT will be advised by the Data and Safety Monitoring Board (DSMB) and will attend the non-voting sessions of the DSMB Meetings. During the study, an external and independent DSMB appointed by the Sponsor will meet to review study data. The board will consist of at least the following voting members:

a Statistician

two independent Medical Experts

The DSMB will meet at least semiannually to assess safety and efficacy data on each arm of the study. The DMSB will operate under the rules of an approved charter that will be written and reviewed at the organizational meeting of the DSMB. At this time, each data element that the DSMB needs to assess will be clearly defined. The DSMB will provide its input to the study Sponsor.

The timing of the DSMB reviews and scope of the data review will be detailed in the DSMB Charter. The DSMB will be required to review the safety and efficacy data upon completion of Day 14 assessments of each cohort, and whenever else as indicated by safety concerns. The DSMB members will also be informed of and review all SAEs and AESIs as and when they are reported. All procedures associated with DSMB reviews, including objectives, data handling and elements for review will be documented in the DSMB Charter. Meeting discussions and decisions will be documented in DSMB minutes. Voting sessions of the DSMB will be attended only by designated DSMB members.

Based on its review, the DSMB will make recommendations to the SRT regarding further conduct of the trial, and if considered necessary, may recommend pausing or stopping further administration of the investigational product. These recommendations will also be communicated to the Ethics Committee and Regulatory Authority as required.

Back to Top

Subject Complaints: Describe procedures (other than information provided in consent document) for handling subject complaints or requests for information about the research. The procedures should offer a safe, confidential, and reliable channel for current, prospective, or past research subjects (or their designated representative) permitting them to discuss problems, concerns and questions, or obtain information.

If the patients have any questions, comments, or complaints regarding any part of the study, or in case of harm related to the trial, or if they have an adverse reaction, they are requested to immediately contact: [name] [name] Address: Asociación Civil Selva Amazónica (ACSA) [name] [contact] E-mail: [contact]

If they have any concerns or questions about their rights as a volunteer in this research, they are encouraged to contact staff at the Comité Institucional de Bioética (CIB) de VÍA LIBRE:

Ethich Committe Chairman: Lic. [name]

Telephone: ([contact] Monday to Friday from 09 am to 18 hrs

• Address: [name]

• e-mail: [contact]

An Ethics Committee is a group of members who are impartial and independent to the medical investigators, and their function is overseeing the respect of the dignity and rights of the participants in the design and performance of the research projects.

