- · The proposed sample composition of subjects.

You may reference grant application/sponsor's relevant protocol pages and attach as an appendix using the below attachment button, however, a summary paragraph must be provided in the text box below.

Proposed dates of enrollment: November 1st, 2020 to December 31st, 2021

The trial will be conducted in Iquitos, Peru. Patients will be recruited from the community, local health-care clinics, and post-secondary educational institutions through word-of-mouth, active recruitment by study staff, and self-referral in response to advertisements. Verbal permission will be sought at private locations where advertisements will be posted, and a signed letter of authorization will be obtained from any performance site where recruitment activities take place. Men and women between the ages of 18 and 70 years with P. falciparum or P. vivax malaria monoinfection living in Peru. 2-6 cohorts of adult patients (10 patients per cohort) with acute,

53333

uncomplicated P. falciparum or P. vivax malaria monoinfection. In total, there will be a minimum of 20 and a maximum of 60 patients. In general, the people who live in these recruitment areas are representative of the general population that suffers malaria in the Amazon region. They are generally mestizo and do not live in extreme poverty. Their educational level includes completion of primary or high school.

Inclusion Criteria:

1) Male or female, aged 18 to 70 years of age (inclusive) at screening.

2) Body weight between 45 kg and 90 kg inclusive

3) Presence of mono-infection of P. falciparum or P. vivax confirmed by:

a. Fever, as defined by axillary temperature = 37.5°C or oral/rectal/tympanic temperature = 38°C, or history of fever in the previous 24 hours (history of fever must be documented) and,

b. Microscopically confirmed parasite infection: 1,000 to 40,000 asexual parasite count/µL blood

4) Written informed consent provided by participant, in accordance with local practice. If the participant is unable to write, witnessed consent is permitted according to local ethical considerations.

5) Ability to swallow oral medication.

6) Ability and willingness to participate and to comply with the study requirements

7) Agreement to hospitalization for at least 102 hours and/or until malarial parasites are not detected by microscopy on 2 consecutive occasions.

8) Agreement to come back to the hospital on Days 7, 10 or 11, 14, 17 or 18, 21, 24 or 25, 28, 35, and 42.

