Cohorts 1a and 1b are expected to achieve roughly five-fold higher plasma exposure of (+)-SJ733 than Cohorts 2a and 2b. Thus, if Cohorts 1a and 1b prove efficacious but repeated drug-related adverse events are observed, the Investigator, DSMB, and SRT may unanimously agree that no further patients should be recruited to Cohorts 1 but that patient recruitment to Cohorts 2 should still be pursued. In this scenario, the Investigator will assess the severity/intensity of the adverse reactions and clinical laboratory changes using the DMID Toxicity Grading Scale for Determining the Severity of Adverse Events provided in Attachment 3 and Section 8.1.2. This information will be relayed to the DSMB and SRT, who will make recommendations regarding further conduct of the trial, and if considered necessary, may recommend pausing or stopping further administration of the investigational product. Cohort progression will only be explored if the Investigator, DSMB, and SRT unanimously agree it is warranted and appropriate. These recommendations will also be communicated to the Ethics Committee and Regulatory Authority and any necessary updates will be made to the patient consent form.

Available Alternative Treatment(s): Describe alternative treatments and procedures that might be advantageous to the subjects, should they choose not to participate in the study. This should include a discussion of the current standard of care treatment(s).

The alternative is to not participate in the study and receive the standard medical attention currently available for the treatment of malaria. If the proposed experimental therapy is ineffective or not tolerated, patients will receive standard treatment from the study physicians following the standard protocol for treating malaria according to current Peruvians standards. Patients maintain the right to withdraw from the study and will receive the standard therapy at the conclusion of the study or at withdrawal to ensure resolution of their malaria. Even if the experimental therapy is effective, all patients will receive the standard therapy at the completion of the trial.

For P. falciparum mono-infection, a combination of Artesunate (AS) and Mefloquine (MQ), known as ASMQ, will be administered as two fixed dose tablets (100 mg AS and 200 mg of MQ) given daily for three consecutive days and supplemented with three tablets (15 mg each) of Primaquine phosphate (PQ) taken on the first day.

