For P. vivax mono-infection, patients will be dosed with 25 mg/kg of Chloroquine (CQ) given over three days (day 1: 4 tablets, day 2: 4 tablets, and day 3: 2 tablets) supplemented with two tablets (15 mg each) of Primaquine phosphate (PQ) taken daily for seven consecutive days.

In the case of P. falciparum and P. vivax mixed infections, the ASMQ treatment regimen will be supplemented with two tablets (15 mg each) of Primaquine phosphate (PQ) taken daily for seven consecutive days.

Back to Top

Research Materials, Records and Privacy: Identify the sources of research material obtained from living human subjects. Indicate what information (specimens, records, data, genetic information, etc.) will be recorded and whether use will be made of existing specimens, records or data. Explain why this information is needed to conduct the study.

Return of Research Results or Incidental Findings (if applicable):

If research has the potential to identify individual results or discover incidental findings that could affect the health of a subject, describe plans to assess, manage, and if applicable disclose findings with individual subjects or provide justification for not disclosing. For IRB expectations, refer to the UK IRB "Frequently Asked Questions (FAQs) on the Return of Research Results or Incidental Research Findings" [PDF].

The medical records gathered during this study will be obtained and processed in electronic form that is used only for investigative purposes related to this study. These records may be reviewed by the Sponsor or their representatives, the, study team, Covance Inc., the Peruvian Ministry of Health through known agencies like the National Health Institute (INS); the Director General autoridad Nacional de Productos Farmacéuticos, Dispositivos médicos y productos sanitarios (ANM) (formerly DIGEMID, the United States Food and Drug Administration (FDA), the regulatory authorities of other countries, and the Ethics Committee (both Peru and the University of Kentucky located in the United States) in order to verify that the study is being carried out in the proper manner.

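### The P. vivax chloroquine course is stated both as 25 mg/kg and as a flat 10 tablets, and these cannot agree across the 45–90 kg entry range

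*Combined protocol and SAP*

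**What the plan says.** The IRB application, section Available Alternative Treatment(s), states the regimen for P. vivax as "25 mg/kg of Chloroquine (CQ) given over three days (day 1: 4 tablets, day 2: 4 tablets, and day 3: 2 tablets", and says that this is "supplemented with two tablets (15 mg each) of Primaquine phosphate (PQ) taken daily for seven consecutive days". The primaquine tablets have a stated strength, as do the artesunate-mefloquine tablets in the paragraph before. The chloroquine tablets do not. No reference weight, weight band or adjustment rule appears in the sentence or anywhere else in the text available for review.

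The same section makes this more than background for people who decline the trial. Participants receive standard therapy if the study treatment is ineffective or not tolerated, and on withdrawal. It adds: "Even if the experimental therapy is effective, all patients will receive the standard therapy at the completion of the trial".

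Inclusion criterion 2 (Study Population) sets the weights concerned: "Body weight between 45 kg and 90 kg inclusive".

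The application also names a governing source. Safety Precautions and Available Alternative Treatment(s) both say that standard treatment follows current Peruvian standards. Safety Precautions adds that, after discharge, it follows the national treatment guidelines under the investigator's supervision.

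**The concern.** A dose proportional to weight and a dose fixed in tablets are different rules. Over an entry range whose upper limit is twice its lower limit, they give different totals to most patients. Because the application says patients will be dosed this way, and applies the therapy to every P. vivax participant at some point, it reads as an operative dosing statement. Two people reading different halves of the sentence could arrive at different chloroquine totals for the same patient.

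What is at stake is mainly patient safety and the internal consistency of a document put to an ethics board. A smaller matter is the safety data: adverse events recorded after standard therapy are harder to interpret when the intended chloroquine total is unclear.

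**Working it through.** **Inputs**
- Weight-based total: 25 mg/kg over three days (Available Alternative Treatment(s)).
- Tablet schedule: 4 + 4 + 2 = 10 tablets (same sentence).
- Body weight W: 45 to 90 kg (inclusion criterion 2).
- Tablet strength s: not stated. It is treated as an assumption and varied from 100 to 300 mg.

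**The plan's own equation.** The sentence implies that 25 × W mg equals 10 × s mg.

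**Weight-based side**
- 45 kg: 25 × 45 = 1,125 mg
- 60 kg: 25 × 60 = 1,500 mg
- 90 kg: 25 × 90 = 2,250 mg

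**Tablet side.** The total is 10 × s, the same for every patient. Setting the two sides equal gives W = 10s / 25 = 0.4 × s, which is one weight for any given strength. To match at 45 kg a tablet would need 1,125 / 10 = 112.5 mg; to match at 90 kg, 2,250 / 10 = 225 mg.

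**Range over the assumed strengths**

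| Assumed s (mg) | Ten tablets (mg) | Weight where both agree (kg) | mg/kg at 45 kg | mg/kg at 90 kg |
|---|---|---|---|---|
| 100 | 1,000 | 40 | 22.2 | 11.1 |
| 150 | 1,500 | 60 | 33.3 | 16.7 |
| 200 | 2,000 | 80 | 44.4 | 22.2 |
| 250 | 2,500 | 100 | 55.6 | 27.8 |
| 300 | 3,000 | 120 | 66.7 | 33.3 |

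Whatever the strength, ten tablets deliver twice as many mg/kg at 45 kg as at 90 kg, because 90 / 45 = 2.

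**Most favourable strength.** The largest relative error over the range is smallest when the excess at 45 kg equals the shortfall at 90 kg: 0.4s/45 − 1 = 1 − 0.4s/90, so 0.4s = 60 and s = 150 mg. The errors are then 33.3/25 − 1 = +33% at 45 kg and 16.7/25 − 1 = −33% at 90 kg.

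**Rounding to whole tablets.** At s = 150 mg, 25 mg/kg rounds to ten tablets only for weights between 9.5 × 150/25 = 57 kg and 10.5 × 150/25 = 63 kg. The same rule calls for 1,125/150 = 7.5 tablets at 45 kg and 2,250/150 = 15 at 90 kg. Rounding widens the point of agreement to a narrow band and does not remove the conflict.

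**Daily split.** Dividing 25 mg/kg in the ratio 4:4:2 gives 10, 10 and 5 mg/kg. The tablet pattern is therefore a coherent three-day division of the weight-based course for a patient at the one matching weight.

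**The case against.** The strongest reply is that the sentence describes usual care and does not govern dosing. It answers a form prompt about alternatives to participation, and the application elsewhere hands treatment to national standards and the study physicians. The tablets may simply show how the course is divided for a reference adult. The 4:4:2 split fits that, and the neighbouring regimens are also given as flat tablet counts. The full clinical protocol is attached to the application but not reproduced in the reviewed text, so strength or weight bands may be settled there.

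Much of this stands. A reader might infer that participants would in fact be misdosed. The documents do not support that: nothing says staff dose from this summary, and a governing guideline is named. A reader might also infer that safety and laboratory data to Day 42 are compromised for all P. vivax patients. That does not follow either. Patients who neither fail nor leave early receive standard therapy at completion, and the last clinic visit is Day 42, so their scheduled laboratory tests are not taken after a chloroquine course. For patients treated earlier, standard therapy complicates later safety data however the chloroquine is counted.

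Two things remain. The sentence says patients will be dosed this way and carries no qualifier marking the tablets as an example. Deferring to a guideline also does not make the stated regimen agree with itself.

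**Conclusion.** The inconsistency is real and minor. The conflict does not depend on tablet strength: over 45–90 kg a flat count of ten tablets and a 25 mg/kg total agree at one weight at most, or in a narrow band after rounding. The ±33% figure rests on an assumed 150 mg tablet, which is the strength most favourable to the sentence; at the other strengths in the table the worst error is larger. These are discrepancies between two written rules at the entry limits, not estimates of dosing error in practice.

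The trial's efficacy inference is untouched. A patient given standard therapy after meeting a failure criterion already counts against crude ACPR under the SAP definition. The 8/10, 6–7/10 and 5/10 progression guidelines and the sample size do not involve chloroquine. Any effect on safety data is confined to patients treated before Day 42, or to the reporting window after participation given under Data and Safety Monitoring (7 days for non-serious events, 30 days for serious ones).

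The documents do not show which half of the sentence is intended, and no view is taken on that.

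**What to change.** Reconcile the mg/kg statement and the tablet schedule in Available Alternative Treatment(s) with each other, with the 45–90 kg entry range and with the national guideline to which the application defers. State the chloroquine tablet strength, as is already done for the other drugs in that section, and say whether the tablet count is only an illustration for a reference adult and, if so, at what weight. Check whether the attached clinical protocol or the consent forms repeat the sentence, and align them if they do.

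The cost is about one corrected sentence. No analysis, endpoint definition or sample size needs to change.
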